8.4 Randomisation

Patients will be sequentially allocated in their respective group, following the algorithm depicted in Figure 8.2.1.

Central randomisation will be implemented by means of RTSM Rave, for full details on how the randomization lists are created and block selection see the randomization plan. In groups 1-3, patients will be assigned to the experimental or the control arms at a 1:1 ratio. Stratification will be performed in the randomised groups. The ISARIC-4C mortality score will be used as a stratification factor in all groups (score <9/ \geq 9). In addition, the type of graft (allogeneic haematopoietic/lung or intestinal/other) will be used for Group 1, whereas the underlying disease will be considered for Groups 2 and 3. For Group 2, the factor categories will be haematological neoplasm vs other disease; the respective categories for Group 3 will be neoplasia vs other. Stratification is not applicable in the non-randomised Group 4.

Day 1 is defined as the day of randomisation. Treatment must start within the same natural day.

8.5 Sample Size Calculation

A) Randomised groups (1-3)

Patients in three of the four groups will be randomly assigned to one of two arms. Each randomised group will have a sample size of 40 patients (20 in the experimental arm, 20 in the control arm).

Given the exploratory nature of this phase II study, this sample size has been chosen based on operational considerations to allow the feasibility of accrual in this relatively small population and also

provide preliminary estimates to establish an updated prior distribution of the mortality rates for further investigation using Bayesian methods in a potential Phase III study.

The operating characteristics of the calibrated Bayesian hierarchical model (CBHM) described by Chu and Yuan (1) have been investigated by means of the CBHM package from Yuan at MD Anderson Cancer Center (2), and with reference to the JAGS program running in R version 4.2.1 (3) on Microsoft Windows 10.

Within the CBHM simulations, 5000 Markov-chain Monte Carlo (MCMC) repetitions per scenario were simulated with a range of operating characteristics for the null, alternative and true mortality rates moving from 5% to 95% in steps of 5% (Table 1). A maximum sample size of 40 per randomised group was set through the CBHM simulations, which in turn determines whether there is a need for the total sample size to be allocated. Within all simulations, the full 120 patients were used, suggesting that this is the minimum sample size that enables decision-making. As an example, if the mortality rate in each group is 20% and we target a clinically meaningful absolute reduction of 12.5% in the experimental arm ($H_0=20\%$, $H_1=7.5\%$), and the assumed true mortality rate is 7.5%, the simulation demonstrates that a sample size of 40 per basket will allow for a posterior probability around 0.9 in each basket (i.e. 90% probability that the experimental arm is better than the control in each basket), ranging from 0.87 (when the data from the fastest basket is analysed) to 0.915 (at the end of the accrual of the last basket) (type I error rate= 0.05).

Table 1 Example of simulated posterior probabilities for sample size definition.

Mortality rate –control arm (null)	Mortality rate – experimental arm (alternative)	True mortality rate	Sample size per basket	Posterior probability 1st basket	Posterior probability 2nd basket	Posterior probability 3rd basket
20%	7.5%	7.5%	30	0.82	0.84	0.865
20%	7.5%	7.5%	40	0.87	0.88	0.915
20%	7.5%	7.5%	50	0.895	0.905	0.93
20%	7.5%	7.5%	60	0.905	0.925	0.97
20%	7.5%	7.5%	70	0.945	0.98	0.985
20%	7.5%	7.5%	80	0.96	0.985	0.985

B) Non-controlled group 4

Clinical conditions that cannot be classified into one of the 3 randomised groups will be pooled into a fourth group of 30 patients. As this group is likely to be characterized by high heterogeneity, it will not have a control arm and will provide safety data on plitidepsin.. A Fleming’s phase II procedure with a 1-stage design has been used to estimate the sample size needed to rule out that plitidepsin induces drug-related SAEs in at least 35% of the patients (null hypothesis), and to confirm that the respective rate is 10 % or lower (alternative hypothesis), with a type I error of 0.05 and a power of 90%.

If at least 25 patients out of a total sample of 30 do not experience a drug-related SAE, the null hypothesis will be rejected.

8.6 Population Sets

Immunocompromised adult patients with symptomatic COVID-19 requiring hospital care.
Patients must fulfill all the inclusion/exclusion criteria to be eligible to participate in the study.

8.6.1 Replacement of Patients

No patients will be replaced. For each group 1-3, all efficacy analyses will be done on Full Analysis Set (FAS) population (See 8.6.2.1 below).

Therefore, accrual in each group will end when the target number of evaluable patients in the FAS population has been reached.

8.6.2 Populations

The design of the trial, the Bayesian analysis and the sample size is based on the 30-day (+/- 2 d) survival information on the FAS population. The analysis of the primary and other time-to-event efficacy endpoints will be performed primarily in the FAS but also in the Per Protocol and 'As treated' populations. Supportive analyses will be performed on the Per Protocol (PP) population. Safety endpoints analyses will be based on the "As treated" population (also known as safety population). If there is any patient randomized by error in a different cohort that its correspondent cohort, for the analysis this patient will be moved programmatically to the valid one.

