8.2 Overall Design

This is a multi-centre, randomised, controlled, open-label, pragmatic, phase 2 basket study to assess the efficacy and safety of plitidepsin in different groups of immunocompromised patients with coronavirus disease 2019 (COVID-19) who require hospital care.

More than 50 sites are planned to participate in this study worldwide.

[figure not shown]
Approximately 150 patients are foreseen for the study, divided in 4 different groups of immunocompromised patients:

- Group 1 –Patients receiving immune-suppression due to haematopoietic or organ transplantation.

- Group 2 – Patients receiving B-cell depleting therapies.
- Group 3 – Patients receiving other immune-suppressive therapies.
- Group 4 – Other situations with immune deficiencies.

Whenever a patient can be allocated to more than 1 group, the priority will be group 1 > group 2 > group 3 > group 4. In groups 1, 2, and 3, patients will be randomised to receive best standard care (BSC) ± other antiviral (if clinically indicated) on control arm and BSC + plitidepsin on experimental arm. Group 4 will not be controlled (it was not applicable in Spain), as shown in Figure 8.2.1.

Figure 8.2.1. Algorithm for Patient Assignment in NEREIDA Basket Trial.

Stratification:

- Group 1: ISARIC mortality (<9/≥9) | Type of graft (allogeneic haematopoietic/lung or intestinal/other)
- Group 2: ISARIC mortality (<9/≥9) | Disease (haematological neoplasm/other)
- Group 3: ISARIC mortality (<9/≥9) | Disease (neoplasia/other)
- Group 4: Not applicable

Study periods:

The study will include a Screening period, a Treatment period and a Follow-up period.

Refer to the Schedule of Assessments (Protocol Appendix 13) for data to be collected.

The Screening period starts once the patient has provided written informed consent and ends when the patient is randomized (allocated in group 4) in the study. Parameters assessed during this time will serve as the baseline values. The screening procedures should be preferably performed within 24 h prior to administration of study treatment, allowing a maximum of 48 h prior to administration of study treatment if required.

The Treatment period starts on Day 1 (date of randomisation) to 24 h after the last dose of the antiviral therapy; if no antiviral was given in the control arm, then the treatment period will finish on Day 4, for data management purposes. Antiviral treatment must always be started on the randomisation date.

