- The development of plitidepsin is discontinued;
- Any other reason (e.g., best interest of the patients, accrual rate makes the completion of the study feasible, etc.) leads to this suspension or termination.

The Sponsor has decided to terminate the study due to low accrual rate.

Blinding/Unblinding

For randomization purposes, no statistical personnel can access the RTSM Rave system.

For IDMC procedures, an independent team outside the scope of this SAP was created following the IDMC Charter.

For the clinical database, PharmaMar Biostats team remains blinded until the results of the analysis are released. Meanwhile, blinded outputs and datasets will be created by ICON Statistics & Programming department for PharmaMar. The procedure planned to blind data for dry-run review consisted of shuffling data and not including outputs with any CRF information where treatment arm is detailed (see below the specific CRF forms). However, given the early termination of the study, there is no risk of bias in the knowledge of randomization lists by the study personnel once the recruitment period has ended. Therefore, on 19/March/2024 it was decided to unmask data and continue with unblinded procedures.

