8.6.2.1 Full Analysis Set (FAS) Population

All randomised patients who have taken at least 1 dose of study treatment (plitidepsin or control) and have completed follow-up for survival until day 30 (± 2). Patients who die before the end of follow-up period will also be included in the FAS population. FAS population will be analysed according to their randomised treatment arm.

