8.6.2.2 As Treated Population

All patients who received any exposure to study treatment (plitidepsin or control). As Treated population will be analysed according to the treatment they actually received.

Day 1 therapy is defined as any exposure to study treatment (partial or complete).

<NOTE: Due to the premature study closure no PP specific outputs or sensitivity analyses will be generated in populations other than the FAS for baseline and efficacy analyses and safety population for safety analyses>.

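### The SAP's rule for moving misclassified patients to the correct cohort is not limited to randomised Groups 1 to 3, so a randomised patient can be moved into uncontrolled Group 4

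*SAP*

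**What the plan says.** SAP 8.6.2 (Populations) opens the rule with "If there is any patient randomized by error in a different cohort that its correspondent cohort" and concludes that "for the analysis this patient will be moved programmatically to the valid one". It names no groups and makes no exception for Group 4. It does not say who determines the valid cohort, from which data or by when, and it asks for no listing. The protocol's own section on analysis populations (8.2) has no such rule.

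Four other places bear on how the rule works:

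- SAP 8.4 allocates Groups 1 to 3 in a 1:1 ratio and says "Stratification is not applicable in the non-randomised Group 4". SAP 8.2 adds that Group 4 has no control and was not applicable in Spain.
- SAP 8.6.2.1 restricts the Full Analysis Set (FAS) to randomised, treated patients with Day 30 survival follow-up (or earlier death), and states "FAS population will be analysed according to their randomised treatment arm".
- SAP 8.6.2.2 does not restrict the safety set to randomised patients: "As Treated population will be analysed according to the treatment they actually received".
- SAP 8.2, describing the screening period, says that it "ends when the patient is randomized (allocated in group 4) in the study".

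On timing, SAP 8.2 records that "on 19/March/2024 it was decided to unmask data and continue with unblinded procedures". The SAP version carrying the rule is dated 20 March 2024.

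**The concern.** Correcting a patient's group is reasonable when every possible destination is randomised in the same way. Group 4 is different: it has one arm and no randomisation.

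The border is easy to cross by mistake. Under protocol 4.1, Group 3 requires immunosuppressive therapy within the last 30 days, while Group 4 takes, among others, haematological neoplasia not currently under treatment. A patient with such a neoplasia whose last therapy falls outside the window could be randomised in Group 3 and later be found to meet only Group 4 criteria. SAP 8.6.2 then moves that patient out of the randomised comparison. A control patient moved in this way has no column to go to, and in Spain the destination group does not exist.

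The trial is open label and its data have been unmasked. Without a requirement to decide from baseline data alone, a reassignment could be influenced by arm or outcome. SAP 6.0 still offers the descriptive tables as a numerical comparison of the arms, so who is in each cell matters even without a test.

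**Working it through.** The plan gives no figure for this rule. The check sets the texts side by side for each direction of movement. The simulation, the mortality rates and the numbers of moved patients are assumptions made for illustration.

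**1. Moves among Groups 1 to 3.** All three groups are randomised 1:1, group is a baseline fact, and the FAS keeps the randomised arm. A simulation under no treatment effect used three groups of 40, 10% misfiled, assumed mortality of 10%, 20% and 30%, and 6,000 trials. After the moves, the mean difference between arms in one group was +0.002 (Monte Carlo SE 0.002). The arms differed in size by about 2 patients on average (95th percentile 5). There is no bias.

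**2. Moves out, from Groups 1 to 3 to Group 4.** The rule covers these patients literally, because they were randomised. It has no arm condition, so both arms lose patients. The same simulation, with misfiled patients sent to Group 4 (assumed mortality 35%), gave a mean difference of -0.001 (SE 0.002). The average size imbalance was about 1.5 patients (95th percentile 4). At 10% misfiling the loss is 0.10 × 40 = 4 randomised patients per group. There is again no bias, provided the decision ignores arm and outcome.

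If that condition fails, one patient is 1/20 = 5% of a full-size arm. Start from 4/20 v 4/20 (20.0% each). Removing only one plitidepsin patient who died gives 3/19 = 15.8% v 20.0%, a gap of 4.2 points. Removing one death from each arm gives 3/19 v 3/19, no gap. The 4.2 points are a worst-case single move, not an expected bias.

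**3. Control patients counted in Group 4.** SAP 8.5 rejects a drug-related SAE rate of at least 35% if at least 25 of 30 patients are free of such an event. Its figures can be checked:

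- alpha = P(X ≥ 25 | n = 30, p = 0.65) = 0.023
- power = P(X ≥ 25 | n = 30, p = 0.90) = 0.927

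Both meet the stated 0.05 and 90% as bounds. A control patient cannot have a plitidepsin-related SAE. If k of the 30 are controls, alpha becomes P(X ≥ 25 - k | n = 30 - k, p = 0.65):

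| k | 0 | 1 | 2 | 3 | 4 |
|---|---|---|---|---|---|
| alpha | 0.023 | 0.030 | 0.039 | 0.051 | 0.065 |

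This matters only if the 25-of-30 rule is still applied. SAP 6.0 says that no formal significance tests will be presented.

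**4. Moves in, from Group 4 to Groups 1 to 3.** For efficacy the text argues against this. The rule speaks of patients randomised by error, SAP 8.4 calls Group 4 non-randomised, and the FAS holds randomised patients only. Two things leave the question open: the wording in SAP 8.2 that sets allocation to Group 4 beside "randomized", and the As Treated set, which takes in any exposed patient.

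This is the only direction that puts unrandomised patients into a comparison. With k such patients of mortality q added to 20 plitidepsin patients at 20%, the shift in that arm is (20 × 0.20 + k × q)/(20 + k) - 0.20:

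- k = 1, q = 0.05: 4.05/21 - 0.20 = -0.7 points
- k = 4, q = 0.05: 4.20/24 - 0.20 = -2.5 points
- k = 4, q = 0.40: 5.60/24 - 0.20 = +3.3 points

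**5. Would any other output show the effect?** The notes in SAP 8.6.2.2, 11.6 and 11.8 withdraw per-protocol and sensitivity outputs. No table by group as randomised is promised.

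**The case against.** The strongest reply is that the rule is close to harmless as it stands. It has no arm condition, the correct group follows from dated eligibility criteria and a fixed priority order, and the move is made by program. Removing patients from both arms on a baseline fact does not bias the comparison, as the simulation shows. Group 4 patients were never randomised, so on a plain reading neither the rule nor the FAS reaches them. Results are descriptive: SAP 11.6 drops the Bayesian model and combines cohorts only for safety. SAP 11.4 already treats failure to meet entry criteria as an important deviation and reviews deviations leading to exclusion before database lock. The number of misplaced patients may be zero.

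Most of this stands, and it rules out two stronger readings.

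- A reader might infer that the rule breaks the randomised comparison, or acts only on the plitidepsin arm. The text does not support that: moves out apply to both arms, and moves in are barred from efficacy on the plainer reading.
- A reader might infer from the dates that the rule was written after unmasking. The change history describes version 3.0 only as an abridgement for early closure, and earlier versions are not available, so nothing shows when the sentence was added.

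Three points remain. The destination of a control patient is undefined. The absence of bias depends on a condition that the SAP does not impose. The deviation review in SAP 11.4 concerns exclusions from populations and does not ask for a list of reassignments.

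**Conclusion.** The concern holds in a limited form. SAP 8.6.2 should not apply across the border between Groups 1 to 3 and Group 4. Applied literally, it loses randomised patients from the comparison and can place a control patient in a group with no control arm. For safety tables, and less plausibly for efficacy, it can also be read to bring an unrandomised Group 4 patient into a randomised group's plitidepsin arm. It sets no safeguard against decisions made with arm and outcome known.

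The likely size is small. Moves on baseline facts in both arms do not bias the comparison. Each patient is 5% of an arm at the planned 20, and more in the smaller groups actually recruited (SAP 11.6 reports low recruitment in cohorts 1 and 3). The documents do not give the number of patients affected, so no actual distortion can be claimed.

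**What to change.** Replace the sentence in SAP 8.6.2 with:

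> Misclassified patients are reassigned only among Groups 1-3, keeping the randomised arm, using data dated before randomisation and without reference to arm or outcome. A randomised patient who meets only Group 4 criteria stays in the randomised group and arm and is listed as an eligibility deviation. A patient allocated to Group 4 is never moved into a randomised group, for efficacy or safety comparisons.

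Add a listing of every reassignment with its reason.

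The cost is one SAP paragraph and one listing, with no effect on treatment or data collection. The small downside is that a few patients remain in a group whose definition they do not meet; the deviation listing makes them visible.

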8.6.2.1 Full Analysis Set (FAS) Population

All randomised patients who have taken at least 1 dose of study treatment (plitidepsin or control) and have completed follow-up for survival until day 30 (± 2). Patients who die before the end of follow-up period will also be included in the FAS population. FAS population will be analysed according to their randomised treatment arm.

8.6.2.2 As Treated Population

All patients who received any exposure to study treatment (plitidepsin or control). As Treated population will be analysed according to the treatment they actually received.

Day 1 therapy is defined as any exposure to study treatment (partial or complete).

<NOTE: Due to the premature study closure no PP specific outputs or sensitivity analyses will be generated in populations other than the FAS for baseline and efficacy analyses and safety population for safety analyses>.

9.0 Conventions and Derivations

Variables reported with different units will be homogenized to standardized variables following the International System of Units (e.g. laboratory tests, biometrical assessments...) unless otherwise specified.

By default, all results will be rounded to one decimal place, except when variables are integer, which will be reported without decimals (e.g., age in years). Percentages for 0 counts will not be presented and 100% values will be presented with no decimal places. For representing p-values four decimals will be selected as default but they could be rounded to fewer decimals if necessary.

Missing values will not be included in the calculation of outputs. Unless otherwise noted, missing data will not be imputed or carried forward.

For patients who discontinue treatment due to adverse events (related or not to study treatment) every effort should be made to remain under study follow-up, anyway, if information is lost before day 28 the conservative value of death will be also imputed.

Patients with no available data for any time-to event efficacy endpoint will be censored at time 0. EOS: Day 60 (± 3) or date of early study termination, if applicable. Patients not yet achieving the time to event endpoint will be censored at the last valid assessment prior to EOS. Efron's method will be used to handle ties.

Assessment windows as specified in the clinical protocol will be respected, see protocol Appendix 13 'Schedule of Assessments and Procedures' for definitions of trial days. Baseline is defined as latest test performed between screening and drug administration.

Change from baseline (%) is defined as: $(\text{test value} - \text{baseline value}) / \text{baseline value} \times 100$.

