7.1.4 Other Efficacy Assessments

The study day (from Day 1 to Day 60 (± 3 days)) on which the following events occurred will be recorded:

- Initiation of supplemental oxygen (of any type)
- Discontinuation of supplemental oxygen (of any type)
- Initiation of respiratory support
- Discontinuation of respiratory support
- Initiation of antivirals or immune-modulating drugs
- Discontinuation of antivirals or immune-modulating drugs
- ICU admission
- ICU discharge
- Subsequent hospital admission for COVID-19 signs or symptoms
- Hospital discharge
- Death

Additionally, the following information will be gathered for each patient on Days 4, 8 (± 1 day), 15 (± 1 day), and 30 (± 2 days) (yes/no):

- Receiving supplementary oxygen therapy
- Receiving high-flow oxygen
- Receiving non-invasive mechanical ventilation
- Receiving invasive mechanical ventilation or ECMO
- Requiring hospital admission related to COVID-19
- Requiring ICU admission
- Receiving subsequent antiviral therapies or immunomodulatory
- Occurrence of new infection
- Death

Based on these data, secondary endpoints for percentages of patients requiring oxygen therapy or different types of ventilation will be calculated and the time (in days) to sustained hospital discharge or withdrawal of supplemental oxygen therapy, percentages of patients with new infection or receiving subsequent antiviral or immunomodulatory therapies, hospitalisation in ICU, and hospitalisation will be measured.

Laboratory based efficacy assessments that are to be performed during the study include:

- Proinflammatory biomarkers: (CRP, LDH, ferritin, cytokine multiplex Luminex[®] panel, including IL-1 β , IL-6, IL-10, and TNF α) in each study arm from baseline (Day 1 prior to start of the study treatment) to on Days 4 (± 1 day), 8 (± 1 day), 15 (± 1 day), 30 (± 2 days), and 60 (± 3 days),
- Anti-SARS-CoV-2 serologic and cellular response will be centrally assessed by validated tests, on Days 1, 30 (± 2 days), and 60 (± 3 days).

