9.1 Imputation in Incomplete Dates

Dates of certain historical or current clinical activities are key component for statistical analysis. An incomplete date results from a missing day, month or year; in that case, the missing figure can be imputed allowing for the calculation of variables, such duration and time to certain event. However, when all of them, day, month and year, are missing no imputation will be done.

Before randomisation/treatment start date

All variables needed to summarize for example prior information where partial information is available will be subject of imputation by means of SAS programming. If the day of a date is unknown then the imputed day will be 1, if the month is also unknown then the imputed date will 1/July. This assumption will be valid if the imputed date is earlier than the randomisation date; otherwise, the imputed date will be the first day of the month of the randomisation date (i.e. 01/Randomisation month date/year).

Between treatment start and end of treatment

All date variables during treatment where information is needed and is not fully available, for example adverse events or concomitant medications, will be subject of imputation by means of SAS programming. If the day of a date is unknown then the imputed day will be 1, if the month and/or year is also unknown then the imputed date will be 1/January (this assumption will be valid if the imputed date is earlier than the treatment start date; otherwise, the imputed date will be the treatment start date). For treatment emergent AEs/CMs a conservative approach will be taken and if imputed date may be considered treatment emergent or medication taken on treatment then always will be counted.

After end of treatment

A conservative approach for the variables collecting information after end of treatment where partial information is available will be imputed by means of SAS programming. The following rules will be implemented: if the day of a date is unknown then the imputed day will be 1; if the month is also unknown, then the imputed date will be 1/July. This assumption will be valid if the imputed date occurs later than the last drug administration date; otherwise, the imputed date will be the last drug administration date plus 1 day.

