11.8 Summary of Statistical Tests

All the main characteristics for estimands to fulfill study objectives will be defined as footnotes in each table following a similar structure than primary estimand definition. Below it can be found the endpoints to measure the variable definition and the analysis method to be used. Treatment attribute is maintained as 'participants will be randomised to receive plitidepsin versus control in each group' whereas applicable and sensitivity analyses according populations defined in 8.5 will be calculated. For intercurrent events, while applicable, a treatment-policy strategy as defined for the primary estimand will be followed.

Table 3 Summary of statistical tests

Endpoints	Analyses	Population
Efficacy primary endpoint		
1-month all-cause mortality rate.	-Frequencies	-FAS population
Key secondary endpoint		
Time to confirmed negativisation in SARS-CoV-2 antigen test or RT-PCR Ct > 30.	-Kaplan-Meier (unstratified)	-FAS population

Endpoints	Analyses	Population
Efficacy secondary endpoints		
Time to sustained end of COVID-related hospital care from the time of randomisation. Sustained discharge is defined as no subsequent admission within 30 days of initial end of hospital care [up to day 60 (± 3)], related to either COVID-19 or COVID-19 therapy	-Kaplan-Meier (unstratified)	-FAS population
Time to sustained improvement (defined in Protocol Section 7.1.3) and resolution of selected COVID signs/symptoms (See Protocol Appendix 10 - COVID-19 signs/symptoms checklist).	-Kaplan-Meier (unstratified)	-FAS population
Distribution of patients according to their clinical status by the 11-category WHO Clinical Progression Scale, at Days 4 (± 1), 8 (± 1), 15 (± 1), 30 (± 2), and 60 (± 3) (See Protocol Appendix 1 – 11-Point World Health Organization (WHO) Clinical Progression Scale).	-Frequencies	-FAS population
Percentage of patients requiring oxygen therapy on Days 4 (± 1), 8 (± 1), 15 (± 1), 30 (± 2), and 60 (± 3).	-Frequencies	-FAS population
Time to sustained discontinuation (i.e., at least 7 days) of oxygen supplementation.	-Kaplan-Meier (unstratified)	-FAS population
Safety secondary endpoints		
Treatment-emergent adverse events (TEAEs).	-Frequencies (severity grade by NCI-CTCAE v5)	-As treated population
TEAEs \geq grade 3 according to the National Cancer Institute	-Frequencies	-As treated population

Endpoints	Analyses	Population
[NCI]-Common Terminology Criteria for AEs (CTCAE v.5.0).		

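### The SAP does not say how patients who have died are counted in the fixed-visit oxygen, ventilation and ICU percentages, so these tables can hide or reverse a mortality difference

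*SAP*

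**What the plan says.** SAP 9.0 sets the general rule in two sentences: "Missing values will not be included in the calculation of outputs" and "Unless otherwise noted, missing data will not be imputed or carried forward".

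Two exceptions are written down. For patients who stop treatment because of an adverse event, SAP 9.0 says that "if information is lost before day 28 the conservative value of death will be also imputed". For partial dates, SAP 9.1 says that "the missing figure can be imputed allowing for the calculation of variables".

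On the analysis set, SAP 8.6.2.1 says: "Patients who die before the end of follow-up period will also be included in the FAS population".

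SAP 11.8, Table 3, lists the visit-day endpoints, for example "Percentage of patients requiring oxygen therapy on Days 4" and the later scheduled days, with parallel lines for advanced support, high-flow oxygen, non-invasive ventilation, invasive ventilation or ECMO, and ICU. Each is to be analysed by frequencies in the FAS. The clinical-status endpoint, "Distribution of patients according to their clinical status by the 11-category WHO Clinical Progression Scale", has the same entry.

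SAP 11.8 applies the primary estimand's treatment-policy strategy to the other endpoints where it fits. That estimand (SAP 11.6.1) names two intercurrent events, treatment discontinuation and starting non-protocol therapy. Death is not among them.

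Protocol 7.1.4 collects yes/no items at Days 4, 8, 15 and 30. "Receiving supplementary oxygen therapy" is one item and death is another. The section does not say how the support items are answered once a patient has died.

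**The concern.** The FAS deliberately includes patients who, at a later visit, can have no oxygen or ventilation status. A programmer working from the SAP alone has two plausible readings. One treats the absent status as missing and drops the patient, which gives a percentage among survivors. The other keeps the patient in the denominator as not receiving support, which puts a death in the same cell as a recovered patient. Neither registers death as a bad outcome.

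This matters because of what is left in SAP version 3.0. There is no model and no test. SAP 6.0 says the descriptive tables are what readers will use to compare the arms numerically, and SAP 11.6 attaches exact confidence intervals to binomial percentages. The choice of denominator is then effectively the whole analysis. Oxygen requirement is an efficacy secondary endpoint, and the other support percentages are secondary or exploratory. A treatment that prevents deaths could show no advantage on them, or could look worse because more of its sick patients are alive to need support.

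**Working it through.** The plan states no expected value for these percentages, so there is no figure to reproduce. The check asks how much the unstated rule can matter.

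**Inputs**
- Mortality *m*: 20% control, 7.5% experimental (example in SAP 8.5).
- Planned size: 20 per arm in each randomised group (SAP 8.5). The formulas below do not depend on it.
- Share of survivors on oxygen at the visit, *s*: not given in the documents. Assumed equal in both arms, 25%, with a range of 0 to 40%.

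**Expected counts at s = 25%**
- Control: 20 × 0.20 = 4 deaths, 16 survivors, 16 × 0.25 = 4 on oxygen.
- Plitidepsin: 20 × 0.075 = 1.5 deaths, 18.5 survivors, 18.5 × 0.25 = 4.625 on oxygen.

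| Handling of deaths | Formula | Control | Plitidepsin |
|---|---|---|---|
| (a) Left out as missing | s | 4/16 = 25% | 4.625/18.5 = 25% |
| (b) Counted as not on oxygen | (1 − m)s | 4/20 = 20.0% | 4.625/20 = 23.1% |
| (c) Death or oxygen | m + (1 − m)s | 8/20 = 40.0% | 6.125/20 = 30.6% |

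**Range over s = 0 to 40%.** The mortality gap is 0.20 − 0.075 = 0.125.
- (a) The gap is always 0.
- (b) The gap is 0.125 × s, from 0 to 5 points, in favour of the arm with more deaths.
- (c) The gap is 0.125 × (1 − s), from 12.5 down to 7.5 points, against the arm with more deaths.

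**Is the direction fixed?** Two examples with whole patients (assumed counts, 20 per arm, 4 deaths v 1 death):
- 8 of 20 dead or on oxygen in each arm. Dropping deaths gives 4/16 = 25.0% v 7/19 = 36.8%, so the arm with more deaths looks better.
- 3 survivors on oxygen in each arm. Dropping deaths gives 3/16 = 18.8% v 3/19 = 15.8%, so the arm with more deaths looks slightly worse. The 3-point gap compares with 7/20 = 35% v 4/20 = 20% for death or oxygen. Coding deaths as no oxygen gives 3/20 = 15% in both arms.

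**Do the stated exceptions close the gap?** The day-28 rule supplies a vital status for one kind of lost patient; it does not give a support status to anyone who has died. The date rule concerns partial dates. The treatment-policy wording covers neither death nor what follows it.

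**The case against.** The strongest reply is that the report as a whole does not hide deaths. One-month all-cause mortality is the primary endpoint, and SAP Table 3 also gives cumulative mortality in the FAS at Days 4, 8, 15, 30 and 60, the same days as the support percentages. Death and its date are recorded, so a programmer can identify who has died at each visit. The study closed early for low recruitment, nothing is formally tested, and no decision rule uses these percentages. All of this stands and limits the impact. It does not supply the denominator of the support tables. A reader can rebuild the number alive and off support by subtraction only if counts are shown and no living patient's status is missing.

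Three stronger readings are tempting, and the documents do not support them.
- **That SAP 9.0 bans all imputation.** It sets a default with stated exceptions. The point is only that none of them reaches status after death.
- **That the arm with more deaths will look better.** The examples above run both ways.
- **That deaths drop out of the WHO-scale table.** The categories are defined in Protocol Appendix 1, which is not in the text reviewed. If the scale scores death, the status is known. What remains to confirm is that the score is entered at every later visit, given the default against carrying values forward.

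**Conclusion.** The gap is real and worth closing. For the fixed-visit oxygen, ventilation and ICU percentages, the SAP leaves open whether patients who have died are dropped or counted as not on support, and neither handling counts death as unfavourable. At the SAP's example mortality rates, with equal oxygen use among survivors anywhere from 0 to 40%, a difference of 12.5 to 7.5 points in death or oxygen becomes either no difference or up to 5 points the other way. These sizes rest on the assumed survivor oxygen use and on mortality rates from the planning example. With unequal oxygen use among survivors the distortion can go in either direction. The actual groups will not match the planned 20 per arm, since SAP 11.6 reports low recruitment in cohorts 1 and 3, and in a smaller arm each death moves a percentage further. The consequence is limited to descriptive secondary and exploratory tables. The primary endpoint and the Kaplan-Meier endpoints are outside this point.

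**What to change.** In SAP 9.0 and Table 3:
1. State that death is not missing data and that, from the date of death, the patient stays in the full FAS denominator at every later visit.
2. For each support endpoint, show three rows by arm and visit: dead, alive on support, alive off support. Report living patients with unknown status separately.
3. Keep the specified percentage requiring support as the endpoint. Give alive and off support as a supplementary row, not as a new headline.
4. Confirm that deaths are scored at every later visit in the WHO-scale table.

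No new data are needed, because Protocol 7.1.4 already records the day of death through Day 60. The cost is SAP wording and table shells. Since SAP 8.2 records the decision to unmask the data on 19 March 2024, the change should be documented as made after that date. That is a further reason to clarify the existing endpoint and not to replace it.
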